2.13.4 Investigators global assessment mod 2011 score and response over time

Treatment Arm A1 will be compared with Arm B1 based on IGA mod 2011 0/1 responses at Week 104 using a similar logistic regression model as described in [Section 2.7.1](#).

Further, IGA mod 2011 0/1 responses at Week 104 will be analyzed by means of logistic regression model similar to the secondary analysis with treatment as a predictor variable and the significant variables among Baseline IGA mod 2011 score, age, and body mass index, and their interactions with treatment. Forward selection procedure based on the likelihood ratio test would be used to select the best subset of covariates. The estimated adjusted odds ratio will be displayed along with the associated 95% confidence interval.

In case of low responses achieved, the logistic regression model may not converge OR in case of non-significant difference between treatment groups any covariate may not get selected in logistic regression model with either of selection method . In such cases, we will use Wald's 1-sided test for comparison of treatment groups in IGA 0/1 score at Week 104.

IGA mod 2011 score will be summarized descriptively, using number and percentages by visits. Confidence intervals for response rates will be derived as well based on the score method including continuity correction ([Newcombe 1998](#)).

For the treatment arms in the Mechanistic Sub-study, the above-stated analyses will also be repeated for both IGA score and IGA mod 2011 0/1 response over the 52 weeks of the Treatment Phase based on the observed data (i.e., until Week 52 for Arms A1b, B1b, and C1, and until

Week 104 for Arms A2 and C2) and Follow-up phase. Summary statistics for IGA mod 2011 0/1 response for treatment phase will also be performed with Non-responder imputation method upto Week 104. For follow-up phase analysis if required separate analysis is performed for change from Week 52 (For Arm A2; Week 104) to post-baseline visits in follow-up phase.

Handling of missing data

Missing IGA 0/1 response values will be imputed with non-response regardless of the reason for the missing data (e.g., premature study discontinuation, missed visit, or administrative issue).

Analysis will be based on the FAS and mFAS.

An analysis for imputed data (NRI approach) will be performed upto Week 104 and based on observed data will be performed upto Week 208.

2.14 Interim analysis and early termination

2.14.1 Interim analysis

An interim analysis for the Mechanistic Sub-study will be performed at Week 16. Subject data of treatment arm A1b, A2, B1b, C1, C2 will only be analyzed.

The Week 16 Interim analysis will be conducted after all subjects have either completed Week 16 or discontinued from of the study or lost to follow up prior to the Week 16. As this analysis at Week 16 will not involve any formal hypothesis testing, no adjustment for multiplicity will be required.

A similar interim analysis for the Mechanistic Sub-study will be performed after all subjects have either completed week 52 or discontinued from the study or lost to follow up prior to the week 52. Subject data of treatment arm A1b, A2, B1b, C1, C2 will only be analyzed.

The Similar interim analysis will be also performed for Week 104 after all subject have either completed Week 104 or discontinued or lost to follow up prior to week 104 .

Efficacy, safety and biopsy data up to Week 16 visit for all subjects will be summarized. AE and topical corticosteroid listing will be presented on the entire treatment phase i.e. reports AE data collected until last subject Week 16 cut-off date.

Following treatment arm will be displayed until otherwise specified Week 16 interim analysis.

1. New onset subjects

Secukinumab(A1b+A2) and nb-UVB (B1b)

2. Chronic subjects

Secukinumab (C1+C2)

Following data points will be analyzed during Interim analysis:

Descriptive statistics , frequency and percentages will be provided for continuous and categorical datapoints respectively.

Following data points will be reported for Screening visit, Baseline visit upto Week 16 visit as applicable.

Demographic, BMI, prior medication, prior plaque-type psoriasis therapy will be displayed for Screening or Baseline Visit as applicable. In prior plaque-type psoriasis therapy, count and percentage for all therapy types and reason of discontinuation will be presented.

Treatment administration of Secukinumab and nb-UVB, Adverse events and serious adverse events will be presented till Week 16 visit.

From efficacy data point PASI score and IGA mod 2011 will be presented for Baseline and Week 16. PASI 75, 90, 100 and IGA mod 0/1 response will be presented for Week 16.

[REDACTED]

[REDACTED]

[REDACTED]

[REDACTED]

[REDACTED]

For the Main study Week 52 and Week 104 IA performed to meet the analysis requirement of analysis endpoints at Week 52 and Week 104. Clinical Study report was prepared for Week 52 primary efficacy analysis.

2.14.2 Early Termination

The study team has made a decision to terminate the study by the end of June 2023 instead of June 2024 (i.e., per protocol expected LPLV) due to the very low number of patients (11) remaining in the treatment-free long-term extension period of the study inability to draw additional meaningful scientific conclusions. The early termination will not have any impact on any of the secondary or primary endpoints, and is not due to any safety concerns. The revised last patient visit (152 week) in the study is projected as 30 Jun 2023 and this date will be considered as the study termination date.

2.15 Additional analyses

Based on the results of Week 104 Main study analysis, it was decided that additional analyses were required without applying imputations and for the subjects who entered the follow-up period. These analyses were added during Week 104 Interim analysis only and were beyond the protocol specified analysis.

These additional analyses were performed only for some efficacy endpoints and based only on the observed data without applying imputation on the subjects who entered follow-up epoch. This additional analysis will consider the hypothesis testing criteria same as for respective endpoints of Main study (i.e. for Key secondary endpoint or exploratory endpoints).

2.15.1 Additional analysis objectives and endpoints

The objectives of this additional analysis are to compare secukinumab (Arm A1) versus nb-UVB (Arm B1) subjects in the follow-up efficacy analysis set with regards to the following items:

1. Proportion of all subjects who achieve at least PASI 90 at Week 104.

3. Proportion of subjects who achieve at least IGA mod 2011 0/1 response at Week 104.

2.15.2 Analysis sets

Two analysis sets will be defined for the additional analysis:

Follow-up Efficacy Analysis Set : Subjects in the mFAS who have at least one PASI assessment after Week 52 up to Week 104, and who have no major protocol deviations based on < PASI50 criteria i.e. Subjects with < PASI50 response at the end of treatment epoch at Week 52 lead to protocol deviations, will be excluded from this analysis set.

Follow-up Safety Analysis Set: Subjects in the mFAS who have at least one safety assessment after Week 52 up to Week 104.

2.15.3 Subject disposition

Subject disposition data will be summarized separately for the additional analysis. All tables, figures and listings mentioned in this section will be based on the Follow-up efficacy analysis set.

Subject disposition will be summarized for follow-up phase as described in [Section 2.3.1](#) for the subjects in follow-up efficacy analysis set.

Primary reason for subject discontinued follow-up phase by week 208, Week 52- Week 104, Week 104-Week 152 and Week 152- Week 208 will be summarized by treatment group.

Median time to event (i.e. study discontinued) after Week 52 and quartiles including 95% confidence intervals will be provided. The confidence intervals will be based on log-log transformation (PROC LIFETEST option conftype=log-log). Completers will be treated as censored. An analysis will be followed as :

- Date of event minus date of Week 52 plus 1 day for subjects experiencing the event
OR
- Date of censoring minus date of Week 52 plus 1 day for subjects not experiencing the event

Time from End of Treatment to Week 52:

Duration between Last dose of Treatment to the Analysis visit Week 52 will be analyzed as ; (Treatment end date -Date of Week 52 + 1) . Summary statistics n, mean, median, SD, Min, Max , Q1 and Q3 of duration of end of treatment to Week 52 is analyzed. Number and percentage of subjects will be displayed for the subjects with duration of > 4 weeks, > 8 weeks , > 12 weeks , > 16 weeks and so on. Analysis to be displayed up to the maximum duration between last dose of treatment to the Analysis visit Week 52 for every 4 weeks.

Subjects with missing visit week 52 date will be excluded from analysis of time to discontinuation and time from End of Treatment to Week 52.

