Subjects who complete treatment phase at Week 52 (for Arm A1 and Arm B1) and Week 104 (for Arm A2) but discontinue before entering follow up phase (despite PASI 50/PASI 90 requirement met) will be assumed as treatment phase completers. The Investigator or Staff will fill additional follow-up disposition eCRF with the reason for discontinuation from the study. In this manner, all the reasons for subjects discontinuation from the study will be captured.

In the Main study for final analysis, subject disposition status with reasons for discontinuation as per CRF will be calculated for duration of Baseline – Week 52. Whereas , for follow-up epoch the duration is Week 52 – Week 104 , Week 104 – Week 152 and Week 152 – Week 208 and for entire follow-up epoch duration Week 52- Week 208. An analysis will be performed for Randomized set and follow-up efficacy analysis set.

For the follow-up epoch, an analysis will be repeated from subgroup of subjects who entered follow-up phase , percentage calculations based on the subject entered follow-up phase. Subject disposition in the follow-up phase for the above mentioned duration (Week 52 – Week 104, Week 104 – Week 152, Week 152 – Week 208) is also performed with respect to the PASI categories (PASI 50-89, PASI 75, PASI 90 and PASI 100) at Week 52. An analysis will be performed for mFAS.

For the mechanistic sub-study, subjects disposition over Screening, treatment and follow-up phase are summarized similarly in separate tables at time of Week 52 interim analysis. However, at time of final analysis and if required at time of Week 104 interim analysis treatment arms are presented separately as per [section 2.1](#). For W104 IA and Final analysis subject disposition status with reasons for discontinuation will be calculated for duration of Baseline – Week 52 , Baseline – Week 104 and Week 52 – W104 for Treatment epoch (Arm A2: Week 104) . Whereas , for follow-up epoch the duration is Week 52 – Week 104 (Arm A1 and B1) , Week 104 – Week 152 , Week 152 – Week 208 and Week 52 – Week 208. For the follow-up epoch, an analysis will be repeated for the subgroup of subjects who entered follow-up phase , percentage calculations based on all the subject entered follow-up phase.

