5.7 Rule of exclusion criteria of analysis sets

Protocol deviations for exclusion from analysis sets are defined in [Table 5-2](#).

Table 5-2 Subject classification rules

Analysis set	Non-PD criteria that cause a subject to be excluded
Full Analysis Set (FAS)	Misrandomized subject
Safety set	Subjects who did not take any study treatment
Modified Analysis Set	Subjects who did not take any study treatment
Follow-up efficacy set	Subject does not have PASI assessment after W52 to W104
Follow-up safety set	Subject does not have Safety assessment after W52 to W104

6 Reference

Clopper CJ, Pearson ES (1934). The use of confidence or fiducial limits illustrated in the case of the binomial. *Biometrika*, 26; 404-413

Newcombe RG (1998) Two-sided confidence intervals for the single proportion: comparison of seven methods. *Statistics in Medicine*; 17:857-872.

Rubin DB (1987) *Multiple imputation for non-response in surveys*. New York: John Wiley & Sons.

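### SAP 2.15.3 measures time to study discontinuation from Week 52 in a set that requires a later PASI, so time in follow-up can be overstated

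*SAP*

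**What the plan says.** SAP 2.15 introduces analyses decided on after the Week 104 results: "additional analyses were required without applying imputations and for the subjects who entered the follow-up period". For disposition, SAP 2.15.3 then fixes the population: "All tables, figures and listings mentioned in this section will be based on the Follow-up efficacy analysis set".

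SAP 2.15.2 defines that set as "Subjects in the mFAS who have at least one PASI assessment after Week 52 up to Week 104", and also leaves out patients below PASI 50 at Week 52. SAP 5.7 repeats the condition as an exclusion rule: "Subject does not have PASI assessment after W52 to W104".

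In the same section, 2.15.3 specifies the time-to-event output: "Median time to event (i.e. study discontinued) after Week 52 and quartiles including 95% confidence intervals will be provided". The clock is "Date of event minus date of Week 52 plus 1 day for subjects experiencing the event", and "Completers will be treated as censored".

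SAP 2.3.1 has related outputs. Follow-up disposition with reasons is given by period on the Randomized set as well as on the Follow-up Efficacy Analysis Set. In addition, "an analysis will be repeated from subgroup of subjects who entered follow-up phase", with entrants as the denominator. SAP 2.3.1 also plans a time to discontinuation that drops only patients without a Week 52 PASI. It states neither the time origin of that analysis nor a restriction to follow-up entrants.

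**The concern.** Membership of the set depends on something that happens after time zero. The clock starts at Week 52, but a patient is admitted only if a PASI is obtained later. Someone who enters follow-up and leaves before giving one is missing from both the risk set and the event count. This is conditioning on the future (immortal time), and it acts on the very event being measured.

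The patients at risk of removal are foreseeable. The first scheduled follow-up visit is Week 64. Under Protocol 5.6.3, no further assessments follow withdrawal of consent, although a final evaluation is to be attempted. Protocol 5.6.4 provides for patients who simply stop attending. Relapsers, by contrast, have all EOS assessments and so will normally qualify. Removal therefore falls mainly on withdrawal of consent and loss to follow-up.

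At stake is how long patients appear to stay in treatment-free follow-up. That description goes into the final CSR, because SAP 2.1 says the report will include the additional analysis. The set also differs from the population named in SAP 2.15, which is those who entered follow-up.

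**Working it through.** The plan states no median time in follow-up and no count of patients without a later PASI, so there is no figure to reproduce. The check covers timing, direction and a range of sizes.

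**1. Timing (SAP Table 2-1).** The Week 52 target is Day 365 and the Week 64 target is Day 449, a gap of 84 days or 12 weeks. Half the gap is 42 days. The Week 52 window for A1 and B1 therefore ends on Day 365 + 42 = 407, and the Week 64 window opens on Day 449 − 42 + 1 = 408, as the table shows. For 12 weeks after the Week 52 target day, a further PASI comes only from an exit or unscheduled visit, or from a Week 64 visit held early.

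**2. Direction and size.** Let q be the share of entrants removed because they left without a later PASI, and S(t) the true retention curve. Once those patients have left, the analysed set shows

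S\*(t) = S(t) / (1 − q),

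which is at or above S(t). Its median is the time at which S(t) = 0.5(1 − q). If leaving is exponential with true median m,

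m\* = m × [1 + log2(1/(1 − q))].

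The value of q is not in the documents. The range of q and the true medians of 26 and 52 weeks are assumptions.

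| q | m\*/m | m\* if m = 26 weeks | m\* if m = 52 weeks |
|---|---|---|---|
| 0% | 1.000 | 26.0 | 52.0 |
| 2% | 1.029 | 26.8 | 53.5 |
| 5% | 1.074 | 27.9 | 55.8 |
| 10% | 1.152 | 30.0 | 59.9 |

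**3. Dependence on exit PASI.** With m = 52 weeks, the share leaving before Week 64 is 1 − 2^(−12/52) = 14.8%. Suppose only those who leave in that interval without an exit PASI are removed. A simulation of 400,000 exponential times gave:

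| Leavers before Week 64 with an exit PASI | Entrants removed | Median in the set (weeks) |
|---|---|---|
| 100% | 0% | 52.0 |
| 90% | 1.5% | 53.2 |
| 75% | 3.7% | 54.9 |
| 50% | 7.4% | 57.9 |
| 0% | 14.8% | 64.0 |

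**4. An undefined term.** The SAP does not say whether a PASI is after Week 52 when it follows the visit date or when it falls beyond the Week 52 analysis window. SAP 2.1.1.5 re-aligns visits to windows, so on the second reading an exit PASI up to Day 407 counts as Week 52. Anyone who leaves in the first 42 days (6 weeks) is then removed even with a complete exit visit. With m = 52 weeks that is 1 − 2^(−6/52) = 7.7% of entrants, and the simulated median is 58.1 weeks.

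**The case against.** The strongest reply is that the protocol already closes the gap. Protocol section 6 schedules an EOS visit, with all final assessments, for anyone who stops early for any reason. Table 6-3 lists PASI at EOS and at unscheduled visits, and Protocol 5.6.3 asks for a final evaluation even on withdrawal. If that works every time, and an exit PASI counts as after Week 52 by visit date, nobody is removed and the bias is zero. This stands as a limit on certainty. A reader might infer that time in follow-up is overstated; the documents support only that it can be, because a planned visit does not guarantee a PASI and no count is given.

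A reader might also infer that early leavers vanish from the report and that relapse will be inflated as a reason for stopping. The documents do not support that for the report as a whole. SAP 2.3.1 gives follow-up disposition with reasons on the Randomized set and among all entrants, so any distortion of reasons is confined to the table on this set. The time to discontinuation in 2.3.1 does not need a later PASI. However, it is not stated to run from Week 52 or to be limited to entrants, so it does not clearly replace the 2.15.3 output.

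A third tempting reading is a biased comparison of Arm A1 with Arm B1. SAP 2.15.3 specifies medians, quartiles and confidence intervals, with no test of duration. Nothing in the documents says which arm would lose more patients without an exit PASI.

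It is also fair to say that describing the Follow-up Efficacy Analysis Set, as the set behind the additional PASI and IGA analyses, is a legitimate use. That justifies a disposition table for the set. It does not justify starting a clock before the patients have qualified.

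**Conclusion.** The point holds for one output: the time to study discontinuation in SAP 2.15.3. Its population depends on an assessment made after its time origin, so the median and quartiles can be too long. Under exponential leaving, the excess in the median is about 3%, 7% or 15% if 2%, 5% or 10% of entrants have no later PASI, and zero if all have one. The true share is unknown.

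The direction assumes that those removed are recorded as leaving early, before the median. It is clearest for withdrawal of consent. For patients lost to follow-up it is less certain, because Protocol 5.6.4 delays calling a patient lost until the scheduled EOS visit has passed. The direction of any difference between arms cannot be stated.

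The output is descriptive and was added after the protocol-specified analyses. It should not be read as a fault in the primary or key secondary test. Leaving out patients below PASI 50 at Week 52 is not part of the problem, since they are not eligible for follow-up.

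**What to change.** In SAP 2.15.3, run time to discontinuation from the Week 52 date on all Arm A1 and B1 mFAS patients who entered the follow-up phase and have a Week 52 date, whether or not a later PASI exists. Count those who leave before a follow-up PASI as events on their discontinuation date.

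Do not define entry as PASI 50 or better at Week 52. SAP 2.3.1 separates patients who met the PASI criterion but discontinued before entering follow-up. Report that group separately.

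State whether after Week 52 means after the visit date or after the analysis window.

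Keep the Follow-up Efficacy Analysis Set for the PASI and IGA summaries and for the disposition table that describes it, with a cross-reference to the all-entrants table in SAP 2.3.1.

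The cost is a few sentences and one more population flag. Reported follow-up times may become slightly shorter. If nobody left without a later PASI, the result does not change.

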5.6 Study completion and discontinuation

5.6.1 Study completion and post-study treatment

A patient will be considered to have completed the study when he or she has completed the last visit planned in the protocol.

Patients who have been screened and have a screening visit recorded in the IRT system at the time that the planned enrolment number is met will be allowed to enter the study and be randomized if they are eligible.

The investigator must provide follow-up medical care for all patients who are prematurely withdrawn from the study, or must refer them for appropriate ongoing care.

For all patients a safety follow-up visit should be conducted (e.g., by telephone) 30 days after the last study visit or 12 weeks after the last dose of study treatment, whichever is later. The information to be collected at this follow-up visit includes concomitant medications, AEs, and survival status.

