5.6.5 Early study termination by the sponsor

The study can be terminated by Novartis at any time for any reason. This may include reasons related to the benefit-risk assessment of participating in the study, practical reasons, or for regulatory or medical reasons (including slow enrolment). Should this be necessary, the patient must be seen as soon as possible and treated as a prematurely withdrawn patient. The investigator may be informed of additional procedures to be followed in order to ensure that adequate consideration is given to the protection of the patient's interests. The investigator will be responsible for informing the IRBs/IECs of the early termination of the study.

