- **Arm B1:** Subjects with new-onset plaque psoriasis will receive either 1 or 2 cycles of nb-UVB of 12 weeks each with a maximum break of 28 weeks between cycles (subjects with PASI 90 at Week 40 will not receive a second treatment cycle). Only during the first 4 weeks of each cycle, nb-UVB treatment will be given in combination with topical calcipotriol 50 µg/g and betamethasone 0.5 mg/g.

Follow-up Phase

At the end of the Treatment Phase at Week 52, all subjects with \geq PASI 50 response from Arm A1 and Arm B1 will enter the Follow-up Phase. Subjects who do not achieve a PASI 50 response, will have all assessments of end of study (EOS) and be discontinued from the study.

[figure not shown]
During the Follow-up Phase, subjects will not receive study treatment; they will be observed maximally until Week 208, and compared regarding the proportion of them who achieve PASI 90 response at Week 104.

Subjects who relapse (those who experience a loss of 50% of the maximum improvement in PASI score achieved during the Treatment Phase) will have all assessments of EOS and be discontinued from the study.

If no relapse occurs, subjects who achieve $<$ PASI 90 at Week 52 in Arms A1 (A1a and A1b) and B1 (B1a and B1b) will be followed until Week 104, while subjects who achieve \geq PASI 90 at Week 52 will be followed until Week 208.

The investigator should provide ongoing adequate care for subjects who relapse. If the investigator decides to continue treating the subjects with secukinumab, a new loading dose of commercially available secukinumab could be considered. The treatment with secukinumab after relapse will be out of scope of the study.

Figure 1-1 Study design – Main study

BL = baseline, EOS = end of study, KSE = key secondary endpoint, nb-UVB=narrow-band ultraviolet B, PASI = psoriasis area and severity index, PE = primary endpoint, R = randomization.

Mechanistic Sub-study

A separate informed consent will be obtained from study subjects who agree on having skin biopsies taken and therefore become eligible for this Mechanistic Sub-study. Besides the biopsies, subjects will undergo the same assessments as in the Main Study.

Treatment Phase

At the Baseline Visit, eligible subjects will be allocated to one of the treatment arms of the mechanistic Sub-study (see [Figure 1-1](#)):

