2.3 Subject disposition, demographics and other Baseline characteristics

2.3.1 Subject disposition

The data of subject disposition will be summarized separately for the Main study as below, unless additional details are stated for the mechanistic sub-study treatment and follow-up phase

will be presented. All tables and listings mentioned in this section will be based on the Randomized set. If required, analysis will be also repeated for the mFAS analysis set.

Screening Phase disposition: The number and percentage of subjects screened, completed and discontinued at Screening with the reasons for screen failures will be presented for all enrolled subjects as captured in the Screening log page of the eCRF.

Since multiple attempts of rescreening are allowed, the rescreening data will be handled in the following approach to ensure that an overestimation of the number of screened subjects is not reported:

- If a subject completes after one or more rescreening attempts and is randomized, he/she will be counted only once as screened and Screening completed and not as a screen failed (as he/she has ultimately met the eligibility criteria and entered the treatment phase)
- If a subject fails after one or more rescreening attempts, He/She will be counted only once as screened and once as screen-failed (although he/she might have failed Screening 2 or more times)
- if a subject is rescreened, only the last available Screening data will be reported.

Treatment and follow-up phase disposition: The number and percentage of subjects in the FAS who completed or discontinued the study periods (i.e., treatment phase at Visit 5 including the reason for discontinuation as captured in the eCRF will be presented by treatment.

Study treatment phase completion:

- Subjects who discontinue at Week 52 (for Arm A1 and Arm B1) due to PASI < 50 and at Week 104 (for Arm A2) due to PASI < 90 will be assumed as treatment phase completers and will not enter into the follow-up period
- Subjects who achieve PASI between 50 and 90 at Week 52 (for Arm A1 and Arm B1) will be assumed as treatment phase completers and enter follow-up period till Week 104.

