Median time to event (i.e. discontinuation) and quartiles including 95% confidence intervals will be provided. The confidence intervals will be based on log-log transformation (PROC LIFETEST option conftype=log-log). Completers will be treated as censored. If any subject whose PASI score is not collected at analysis visit week 52 the subject will be not considered for Time to discontinuation analysis.

In addition, the number and percentage of subjects with protocol deviations will be tabulated by each treatment and deviation category, separately for Main study and Mechanistic sub-study. Subjects excluded from analysis set(s) due to defined Protocol deviations will be tabulated in the same. The number and percentages of subjects in each analysis set will be summarized by each treatment for the FAS, separately for Main study and Mechanistic sub-study. In Mechanistic study for final analysis protocol deviation will be listed only for FAS set. . Covid-19-specific protocol deviations will be tabulated separately in a similar way. Listing will also be produced separately for Covid-19 related protocol deviations.

Caution will be taken in the interpretation of the percentages of subject disposition and protocol deviations due to the overlap of subjects between study arms (A1 and B1) in the Main study and Mechanistic sub-study, as data of these 2 arms will be included in both of the study outputs.

All subjects data related to disposition, protocol deviation and analysis sets will also be listed.

Any possible implications of study changes due to COVID-19 on the interpretation of study subject data will be tabulated and listed.

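### Time to discontinuation in follow-up has no censoring rule for the sponsor's early stop, so up to 11 patients still under observation would count as events together with relapses

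*SAP*

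**What the plan says.** The main disposition analysis (SAP 2.3.1) states: "Median time to event (i.e. discontinuation) and quartiles including 95% confidence intervals will be provided". The additional analysis of the follow-up set (SAP 2.15.3) states: "Median time to event (i.e. study discontinued) after Week 52 and quartiles including 95% confidence intervals will be provided". Both give one censoring rule: "Completers will be treated as censored". The code template in SAP 5.6.4 allows two states, event or no event.

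The SAP uses the word completer only for the treatment phase. For example, patients with a PASI response between 50 and 90 at Week 52 "will be assumed as treatment phase completers and enter follow-up period till Week 104". No definition is given for the follow-up phase.

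Protocol 5.6.1 defines completion of the study: "A patient will be considered to have completed the study when he or she has completed the last visit planned in the protocol". For Arms A1 and B1, the last planned visit depends on the Week 52 response. It is Week 104 below PASI 90, and SAP 1.1 says that those with at least "PASI 90 at Week 52 will be followed until Week 208" if they do not relapse.

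SAP 2.14.2 records that the study was ended early "due to the very low number of patients (11) remaining in the treatment-free long-term extension period", with the last patient visit brought forward to Week 152, projected for 30 June 2023. Protocol 5.6.5 says that on termination by the sponsor "the patient must be seen as soon as possible and treated as a prematurely withdrawn patient". Protocol 5.6.6 makes relapse in follow-up a reason for mandatory discontinuation.

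**The concern.** A relapse and a sponsor stop are different kinds of ending. A relapse tells us how long the treatment-free period lasted. A sponsor stop tells us only that it had lasted at least that long, which is administrative censoring. If both are coded as discontinuation, the Kaplan-Meier curve falls at each stop as if the patient had relapsed or dropped out.

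The patients concerned are among those with the longest treatment-free follow-up, so the distortion falls on the late part of the curve. It is larger in whichever arm had more patients still under observation. The sponsor had an occasion to deal with this: the SAP revision history lists the early-termination text as added on 18 August 2023, before the final database lock, with sections 2.3 and 2.15 also revised. The censoring rule in the current text makes no provision for the stop. SAP 2.14.2 comments only on the primary and secondary endpoints.

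**Working it through.** The plan states no figure for this output, so there is none to reproduce. The check has three steps.

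**1. Who is affected.** The inputs are Week 208 as the last planned visit (SAP 1.1), and Week 152 for the last patient at the stop with 11 patients remaining (SAP 2.14.2).

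- Week 152 is 152 − 52 = 100 weeks after Week 52. Week 208 is 208 − 52 = 156 weeks after it.
- The last patient was therefore cut 208 − 152 = 56 weeks short. Patients enrolled earlier were cut by less, or had already reached Week 208.
- A patient stopped between Weeks 152 and 208 without relapse has not made the last planned visit. He or she is not a completer under Protocol 5.6.1, so is not censored and counts as an event.

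**2. When a quartile can move.** Recoding the stopped patients changes nothing before the first stop, about 100 weeks after Week 52. The upper quartile can change only if the curve is still above 0.25 then, and the median only if it is above 0.50.

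The illustrations below assume relapses spread over 4 to 90 weeks after Week 52, stops spread over 100 to 150 weeks, and no other censoring. N is the arm size, k the number stopped and c the number who reached Week 208. Just before the first stop, S = (k + c)/N. At the end, S = c/N if stops are events and (k + c)/N if they are censored. A quartile is read as the first time at which the curve is at or below its level.

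| N | k | c | S before first stop | Median: event / censored (weeks) | Upper quartile: event / censored (weeks) | Final S: event / censored |
|---|---|---|---|---|---|---|
| 70 | 11 | 0 | 11/70 = 0.157 | 54 / 54 | 81 / 81 | 0.00 / 0.157 |
| 70 | 11 | 10 | 21/70 = 0.300 | 65 / 65 | 115 / not reached | 0.143 / 0.300 |
| 40 | 11 | 0 | 11/40 = 0.275 | 62 / 62 | 100 / not reached | 0.00 / 0.275 |
| 20 | 11 | 0 | 11/20 = 0.550 | 100 / not reached | 125 / not reached | 0.00 / 0.550 |

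As an example of the reading, take N = 40. The first stop coded as an event takes the curve from 11/40 = 0.275 to 10/40 = 0.25, so the upper quartile is 100 weeks. If the stop is censored, the curve stays at 0.275 and the quartile is not reached.

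**3. How often it would move in an arm of about 70.** The simulation used 500 arms per scenario, with 70 patients in each. Of these, 18 were censored at Week 104 because they were below PASI 90 at Week 52. Relapse times were exponential and seen at 12-week visits, all remaining patients were stopped between Weeks 152 and 208, and confidence limits were log-log.

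| Median time to relapse (weeks) | Mean number stopped in the arm | Upper quartile changed | Its upper limit changed |
|---|---|---|---|
| 52 | 10.5 | 59% | 94% |
| 36 | 5.1 | 3% | 43% |
| 24 | 1.7 | 0% | 1% |

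A separate set of 1,000 runs of the same model filled in the middle. With about 8 stopped in the arm the upper quartile changed in 22% of runs, with 6.5 in 9% and with 5 in 2%. The median did not change in any of these scenarios.

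**The case against.** The case on the other side has several parts, and much of it stands.

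- **The coding is inferred.** The SAP nowhere says how a sponsor-stopped patient is coded. The sentence in Protocol 5.6.5 instructs sites on handling patients at termination and is not a survival-analysis rule. A programmer could also treat the revised last visit as completion. This stands as a limit on certainty. It does not remove the problem, because the only definition of study completion in the documents points the other way.
- **It is a disposition output.** The event is discontinuation for any reason, and a sponsor stop is one. No hypothesis test is attached. This stands. A reader might infer that this is the trial's main measure of the length of remission, but the documents do not support that. They never present it so, and blacked-out parts of the SAP may hold a dedicated relapse analysis.
- **The longest remissions need not be involved.** A reader might infer that the plan turns the longest remissions into events. Patients who reached Week 208 before the stop are completers and are censored. Counting 208 weeks back from 30 June 2023 gives early July 2019, and the study was already running at Amendment 02 in September 2019, so such patients may exist.
- **The large percentages are near an upper bound.** They need about 10 stopped patients in one arm when the whole study had 11. Some of those may be in Arm A2, which is also followed to Week 208 but lies outside the comparison of A1 with B1. The simulation also has no patients completing at Week 208.
- **Reasons are already tabulated.** SAP 2.3.1 and 2.15.3 list reasons for discontinuation by interval. That may let a reader see the stops, but the time-to-event rule does not use the reason.

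**Conclusion.** The point holds as a gap that, on the documents' own definitions, leads to administrative endings being counted as events. At most 11 patients are involved, and the documents give neither their arms nor the number who reached Week 208.

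The certain effect of that coding is a lower tail to the curve. The upper quartile and its upper limit may also be shortened. In an arm of about 70 the upper quartile moves mainly if most of the 11 are in that arm, and the median stays where it is. The median could move only where more than half of the curve remains at about 100 weeks after Week 52, as in the 20-patient illustration. These sizes rest on assumed relapse patterns and arm sizes, since the documents contain no event counts. The primary analysis at Week 52 and the key secondary analysis at Week 104 both precede the stop for every patient and are not touched.

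**What to change.** In SAP 2.3.1 and 2.15.3, define a follow-up completer as a subject who has attended the last follow-up visit planned for him or her (Week 104 or Week 208, according to response). Then add: *Subjects whose follow-up ended because of the sponsor's early termination are censored at their last visit.* Show sponsor termination as a separate reason in the follow-up disposition tables, in every interval in which it occurs.

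The cost is two sentences in the SAP and a rerun of the time-to-discontinuation tables, with no new data. If the analysis has already been run, the change and its rationale can go in the clinical study report, as the SAP introduction provides. The downside is that an upper quartile or its upper limit may become not estimable. That would correctly show that follow-up ended before the quantity could be observed.
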